#### **10.2.4 Perioral Lines Severity Scale (POLSS) at Rest Evaluation**

Aesthetic improvement will be determined by the PI's assessment of subjects at Visit 1, Treatment (baseline) and at Visit 4, 14-Day Post-OCR partially through utilizing the POLSS (Appendix H).

## **11 DATA MANAGERMENTS**

### **11.1 Case Report Forms**

For each subject enrolled who has given informed consent, completed the screening process, and began the study process, a Case Report Form (CRF) will be created and signed by the PI or designee to certify completeness and correctness.

If a subject is withdrawn from the study due to a treatment-related AE, due diligence must be used to document the outcome. Source documentation verification will be performed by the study monitors. All CRFs will remain at the study site.

### **11.2 Data Handling**

Data management based on GCP refers to the activities defined to achieve safe routines for efficiently entering clinical data information into a database while avoiding errors. The data management routines include procedures for handling CRFs, database set-up and management, data entry and verification, data validation, and documentation of the performed activities including information of discrepancies in the process.

The database, the data entry screens, and program will be designed in accordance with the study protocol and the CRF. Single data entry and proofreading will be used for data entry and verification. Data validation will be performed after data entry and verification by manual review. When the clinical study coordinator has made all efforts to ensure that the data recorded in the CRFs and entered in the database is as correct and complete as possible, "clean file" is declared, and the database is closed. The clinical study coordinator should document the database closure in a signed written document. Final statistical analysis should be generated using data from the closed database. Any additional subsequent changes or corrections to the closed database should be documented in an audit trail.

### **11.3 Publication**

Following completion of the study, the data may be considered for reporting at a scientific meeting or for publication in a scientific or medical journal.

## 12 STATISTICAL METHODS

### 12.1 Sample Size

20 subjects will be enrolled as described in Section 7. Using the primary end point of FIQ scores, and assuming a standard deviation of 14 and a difference of 2.5 in the total FIQ score between the baseline and 14-Day Post-OCR, a sample size of 20 will provide a power of approximately 8% (with  $\alpha=0.05$ ).

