**Clinical Hypothesis**

Subjects who are treated with Restylane® Silk for lip rejuvenation project a more positive first impression as compared to their pre-treatment baseline. Those who are treated with Restylane® Silk will also report a more positive mood perception after treatment as compared to pre-treatment.

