## 6 STUDY DESIGN

This is an open-label, post-market study to assess the impact of lip rejuvenation with Restylane® Silk on the projected first impression and the self-perception of mood.

20 subjects, at least 21 years of age, who display mild to severe oral commissures or none to severe perioral lines, as judged by the Principal Investigator (PI) utilizing the Oral Commissure Severity Scale (OCSS, Appendix G) or the Perioral Lines Severity Scale (POLSS, Appendix H), will be enrolled.

The study is composed of up to 4 patient visits and a post-visit evaluation of patients' photographs by blinded evaluators. A schematic of the study design is presented in Appendix A.

All subjects who meet the specified criteria, listed in Section 7, will complete the Subjective Happiness Scale (SHS, Appendix B) and the Happiness Measures questionnaire (HM, Appendix C) prior to receiving any treatments. The PI also records the severity of subjects' oral commissures and/or the perioral lines using the OCSS and/or the POLSS respectively. Furthermore, all subjects undergo photo- and videography, as described in Appendix I, prior to treatment.

Subjects will then be injected with Restylane® Silk with a volume sufficient to achieve Optimal Cosmetic Results (OCR), per treating investigator's discretion but not to exceed a total of 4ml (4 syringes). Subjects will be assessed 14 ± 3 days after injection for achieving the OCR. If OCR has not been reached, as judged by the PI, a second, 'touch-up,' injection of Restylane® Silk will be performed.

The final evaluation of subjects will take place 14 ± 3 days after achieving OCR. Hence, this would be 14 ± 3 days after the first injection for those who achieved OCR with one treatment but 28 ± 3 days after the first injection for those who required a 'touch-up' injection. Subjects will complete the SHS and HM questionnaires as well as self-report any aesthetic alterations experienced using the Global Aesthetic Improvement Scale (GAIS, Appendix D). They will also undergo photo- and videography, as described in Appendix I. Furthermore, the PI will rate the subjects on the GAIS (Appendix E) as well as on the OCSS and the POLSS.

Photographs taken at pre-treatment and 14-Day Post-OCR will be randomly divided into 4 binders, for a total of 10 photographs per binder. Each binder will be evaluated at least by 50 blinded evaluators using the First Impressions Questionnaire (FIQ, Appendix F) to rate each photograph.

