## **10 RESPONSE CRITERIA**

### **10.1 Primary Variable Assessments**

The primary assessment of this study is to determine if subjects who receive lip rejuvenation treatment with Restylane® Silk would project a more positive first impression as well as experience a more positive mood perception as compared to their baseline. The primary efficacy will be established by comparing the projected first impression of subjects at 14-Day Post-OCR with that of the baseline. The change in mood perception will be determined by comparing the SHS and HM results from 14-Day Post-OCR with those from the baseline.

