#### **10.1.1 Assessment of First Impressions**

Upon completion of the study, a minimum of 200 blinded evaluators will assess one of four binders, for a minimum of 50 blinded evaluators per binder, each comprised of 10 photographs selected randomly from Visit 1 (baseline) or Visit 4 (14-Day Post-OCR) for each subject. The

FIQ will be completed by each evaluator for each photo (see Appendix F). Each photograph will be graded based on a 10-point numerical rating scale for each of the 8 categories listed below:

- *Social skills*: Social desirability, temperament, positive mood, getting along with others, friendliness
- *Academic performance*: Intelligence, educational skills
- *Dating success*: Frequently invited, lack of dating anxiety, thought of positively after dating encounter
- *Occupational success*: Job performance, competence, motivation for success, suitability as potential employee
- *Attractiveness*: Pleasing appearance
- *Financial success*: Has achieved or is a member of an elevated socioeconomic status
- *Relationship success*: Willingness to compromise put the relationship health before their own desires or gain, Ability to maintain long term friendships
- *Athletic skills*: Ability to excel at athletic events, including individual and team sports

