### 12.4 Methods of Analysis

Descriptive statistics will be used to analyze the data. The number of subjects (n), minimum (min), maximum (max), mean, median, and standard deviation (SD) will be reported for the continuous data. Frequencies and percentages will be reported for the categorical data. Unless otherwise stated, statistical testing will be two-sided and executed using a significance level of 0.05. All statistical analyses, summary tables, and data listings will be performed using the SPSS (IBM) or the Excel (Microsoft Co.) software.

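### The stated 8% power for the FIQ endpoint gives no credit for comparing each subject with their own baseline, and Section 12.1 does not define the SD of 14

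*Combined protocol and SAP*

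**What the plan says.** Section 12.1 fixes the sample at 20 subjects and bases its power statement on the FIQ. It assumes an SD of 14 and a difference of 2.5 "in the total FIQ score between the baseline and 14-Day Post-OCR", with alpha 0.05, and concludes that "a sample size of 20 will provide a power of approximately 8" percent. It names no test and no within-subject correlation. It does not say whether 14 is the SD of the change, of a photograph's score at one visit, or of one evaluator's rating. A literature reference is attached to the assumed difference.

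The comparison is within subject. The Clinical Hypothesis in the synopsis is that treated subjects "project a more positive first impression as compared to their pre-treatment baseline". Section 10.1 establishes primary efficacy by "comparing the projected first impression of subjects at 14-Day Post-OCR with that of the baseline". Section 6 says "Photographs taken at pre-treatment and 14-Day Post-OCR will be randomly divided into 4 binders", with 10 photographs in each. That makes 4 × 10 = 40 = 20 subjects × 2 visits, so both photographs of every subject are rated. Section 10.1.1 provides "for a minimum of 50 blinded evaluators per binder, each comprised of 10 photographs".

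Section 12.4 adds that "statistical testing will be two-sided and executed using a significance level of 0.05". It names no test for the FIQ.

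**The concern.** A power statement should describe the comparison that the trial will make. Here the same 20 faces are rated before and after treatment, and two photographs of one face would normally be expected to score alike. That similarity removes between-subject variation from the change and raises power. A figure of 8% is what one obtains by ignoring it.

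At stake is the accuracy of the only power statement for the FIQ primary endpoint. Neither the paired power nor the precision to expect from 20 subjects can be worked out from Section 12.1, because the one variance figure given is not defined.

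**Working it through.** **Inputs.** From Section 12.1: n = 20, difference 2.5, SD 14, alpha 0.05. From Section 12.4: two-sided testing. From Sections 6 and 10.1.1: at least 50 evaluators per photograph. The within-subject correlation ρ is not in the documents; the values below are assumptions.

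**Step 1: reproduce the stated figure.** For two independent groups of 20, the standardised difference is 2.5 / (14 × √(2/20)) = 2.5 / 4.427 = 0.565.
- Normal approximation: Φ(0.565 − 1.960) = 8.1%.
- Noncentral t, 38 df: 8.5%.

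The figure of about 8% is therefore reproduced by an unpaired calculation.

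**Step 2: other calculations that might give 8%.**
- Paired t-test (19 df), SD 14 at each visit, ρ = 0: SD of change = 14 × √2 = 19.8, power 8.4%. This also fits.
- Paired t-test, SD of change 14: 11.8%. This does not fit.
- One-sided versions: 13.8% (two groups of 20), 10.4% (two groups of 10), 19.1% (paired, SD of change 14). None fits.
- Two groups of 10, two-sided: 5.9% (normal) to 6.7% (t). A poorer match, and also unpaired.

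**Step 3: power and precision for the planned comparison.** Paired t-test, n = 20, 19 df, noncentrality 2.5 / (SD of change / √20). The expected 95% CI half-width is 2.093 × SD of change / √20.

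If 14 is the SD of change, the noncentrality is 0.80, power is 11.8% and the half-width is 2.093 × 14 / 4.472 = 6.6 points.

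If 14 is the SD at each visit, SD of change = 14 × √(2(1 − ρ)):

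| Assumed ρ | SD of change | Power | Half-width |
|---|---|---|---|
| 0 | 19.80 | 8.4% | 9.3 |
| 0.5 | 14.00 | 11.8% | 6.6 |
| 0.8 | 8.85 | 22% | 4.1 |
| 0.9 | 6.26 | 40% | 2.9 |

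Power of 80% needs an SD of change of about 3.79, which means ρ = 1 − 3.79² / (2 × 14²) ≈ 0.96.

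**Step 4: if 14 is the SD of one evaluator's rating.** With 50 independent ratings per photograph and a between-subject SD of true change τ (not given, so assumed), SD of change = √(τ² + 2 × 14² / 50) = √(τ² + 7.84). For τ = 3 this is 4.10 and power is 73%; for τ = 5 it is 5.73 and power is 46%. Power is higher on this reading, but how much higher depends on τ as well as on what 14 means.

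**The case against.** The strongest reply is that little turns on this. The plan openly reports very low power, the sample size does not depend on it, and Section 12.4 is mainly descriptive. On the two subject-level readings, power stays at or below 40% for correlations up to 0.9, so the message is still low power. The corrected figure could even be 8.4%, if the two visits were uncorrelated. All of that stands, and it is why the point is minor. The cited reference may also define the SD. That cannot be checked here, so the claim is only that Section 12.1 does not define it.

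Several stronger readings are tempting, and the documents do not support them:

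- **That an unpaired test was used by mistake.** A paired test with near-zero correlation gives the same figure. The arithmetic is right for its inputs, and the documents do not show which calculation was made.
- **That 8% is a misprint for 80%.** The stated inputs reproduce 8% directly. With SD 14 at each visit, 80% would need a correlation of about 0.96.
- **That power could really be about 97%.** This needs 14 to be a single-rating SD and every subject to have the same true change (τ = 0, SD of change √7.84 = 2.8). Section 12.1 supports neither.
- **That the single-rating figures are too high because evaluators are shared within a binder.** Evaluator effects partly cancel in the before-after difference. In a simulation that assigned half the rating variance to evaluators (an assumption), sharing did not lower power at τ = 3 or τ = 5.
- **That a non-significant FIQ result could not be interpreted.** A completed result is read from its observed estimate and confidence interval, not from the planning SD.

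**Conclusion.** The point holds, at minor severity. The stated power of about 8% does not credit the within-subject design set out in the Clinical Hypothesis and Sections 6 and 10.1. The matching paired figure is 11.8% if 14 is the SD of change. If 14 is the SD at each visit, it is 11.8% to 40% for assumed correlations of 0.5 to 0.9. It is higher still if 14 is the SD of a single rating, by an amount that the documents do not fix. These results assume a two-sided paired t-test at 0.05 on all 20 subjects. The correlations and the spread of true change are assumptions shown as ranges, not values from the plan. Pairing alone does not make the study well powered unless the SD of change is near 3.8.

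**What to change.** Keep 20 subjects.

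In Section 12.1, say whether 14 is the SD of the change, of a photograph's score at one visit, or of a single rating. Replace the 8% with the power and expected 95% CI half-width for the paired, subject-level comparison, and show a range by SD of change (n = 20, difference 2.5):

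| SD of change | Power | 95% CI half-width |
|---|---|---|
| 14 | 12% | 6.6 |
| 8.9 | 22% | 4.2 |
| 6.3 | 39% | 2.9 |
| 3.8 | 80% | 1.8 |

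In Section 12.4, name a matching within-subject analysis. One example is a two-sided paired t-test on the change in each subject's total FIQ score, averaged over the evaluators of each photograph. A mixed model with subject and evaluator effects would also be valid.

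The cost is a revised paragraph in Section 12.1 and one sentence in Section 12.4, with no extra subjects, visits or evaluators.

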### 12.2 Study Population

The study population will include all subjects who are enrolled and have received treatment. The entire study population will be included in the statistical analyses.

### 12.3 Study Endpoints

#### 12.3.1 Primary Endpoints

1. FIQ completed by 200 blinded evaluators using the photos of subjects from the baseline and the 14-Day Post-OCR visits
2. Subjects' execution of the SHS at 14-Day Post-OCR
3. Subjects' completion of the HM questionnaire at 14-Day Post-OCR

#### 12.3.2 Secondary Endpoints

1. S-GAIS evaluation at 14-Day Post-OCR
2. PI-GAIS evaluation at 14-Day Post-OCR
3. OCSS evaluation at 14-Day Post-OCR
4. POLSS evaluation at 14-Day Post-OCR

### 12.4 Methods of Analysis

Descriptive statistics will be used to analyze the data. The number of subjects (n), minimum (min), maximum (max), mean, median, and standard deviation (SD) will be reported for the continuous data. Frequencies and percentages will be reported for the categorical data. Unless otherwise stated, statistical testing will be two-sided and executed using a significance level of 0.05. All statistical analyses, summary tables, and data listings will be performed using the SPSS (IBM) or the Excel (Microsoft Co.) software.

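### Three primary endpoints share a flat 0.05 level with no named score, success rule or multiplicity control; if any one counts, false improvement is about 5.5–7.3% rather than 2.5%

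*Combined protocol and SAP*

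**What the plan says.** Section 12.3.1 lists three primary endpoints: "FIQ completed by 200 blinded evaluators using the photos of subjects from the baseline and the 14-Day Post-OCR visits"; "Subjects' execution of the SHS at 14-Day Post-OCR"; and the subjects' "completion of the HM questionnaire at 14-Day Post-OCR". The last two name the filling-in of a form. They do not say which score, or which change from baseline, is the result.

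Other sections describe the primary endpoint differently:

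- Section 12.1 bases the power statement on one endpoint: "Using the primary end point of FIQ scores". The quantity used there is the total FIQ score.
- Section 10.1 opens by pairing first impression with mood, then says: "The primary efficacy will be established by comparing the projected first impression of subjects at 14-Day Post-OCR with that of the baseline". SHS and HM follow as 10.1.2 and 10.1.3 under the same primary heading.
- The synopsis hypothesis and Section 5 join first impression and mood in one primary objective.

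Section 12.4 begins "Descriptive statistics will be used to analyze the data" and then sets a default: "statistical testing will be two-sided and executed using a significance level of 0.05". It names no test for any endpoint and gives no hierarchy, adjustment or rule for declaring success. No other section supplies one.

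Two of the instruments clearly give more than one score. The FIQ uses a "10-point numerical rating scale for each of the 8 categories listed below" (10.1.1), plus the total used in 12.1. The HM form (Appendix C) has one 0–10 item and three percentages that must add to 100.

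**The concern.** The 0.05 level describes one test. When three endpoints are all called primary and nothing says whether one or all must succeed, the error rate of the primary claim is undefined. It depends on how the results are read once they are known. On the most permissive reading, one significant endpoint out of three is reported as the trial meeting a primary endpoint. Because no score is named within the FIQ or HM, a single FIQ category or HM percentage could serve the same purpose.

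This matters more than usual here because the plan's own power for the FIQ is about 8%. A lone significant result would be hard to tell from chance, and Section 11.3 allows for presentation or publication.

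**Working it through.** **1. Reproduce the plan's own figure.** Inputs from 12.1: N = 20, SD 14, difference 2.5, α = 0.05. The plan states no familywise error rate; its only related figure is the power of about 8%.

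- Unpaired standard error with 20 values per time point: 14 × √(2/20) = 4.43. Ratio: 2.5/4.43 = 0.565.
- Power in the favourable direction: Φ(0.565 − 1.960) = 8.1%. Adding the opposite tail, Φ(−0.565 − 1.960) = 0.6%, gives 8.7%.

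The stated 8% is reproduced on this unpaired basis. (A paired t-test with 14 as the SD of the differences would give 11.8%.)

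**2. Three primary endpoints, any one sufficient, no true effect.** A two-sided 0.05 test puts 2.5% in the improvement direction.

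- Independent tests, either direction: 1 − 0.95³ = 14.3%.
- Independent tests, improvement only: 1 − 0.975³ = 7.3%.
- Correlated tests: the documents give no correlations, so these are assumed. Simulation with 400,000 draws and equal correlations:

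| Correlation | Either direction | Improvement |
|---|---|---|
| 0 | 14.3% | 7.3% |
| 0.3 | 13.6% | 6.8% |
| 0.5 | 12.6% | 6.3% |
| 0.7 | 10.9% | 5.5% |

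The single-test comparators are 5% and 2.5%. Simulated paired t-tests with n = 20 agree to within about 0.3 percentage points.

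**3. Scores available within the instruments.** FIQ: 8 categories + 1 total = 9. SHS: 1, assumed, because its form (Appendix B) is not in the text available for this review. HM: 1 item + 3 percentages = 4. Sum: 9 + 1 + 4 = 14.

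- Independence: 1 − 0.95¹⁴ = 51.2% in either direction; 1 − 0.975¹⁴ = 29.8% for improvement.
- Independence cannot hold. The three HM percentages add to 100, and the FIQ total is taken here to be the sum of its eight categories. Time spent neutral also has no stated direction of improvement. Building in these dependences alone gives about 48% and 27%.
- With that structure, and assumed correlations within the FIQ and within the mood scores both at 0.3 or both at 0.7: improvement 22.6% or 15.4%; either direction 43.9% or 32.7%.
- With 14 equally correlated paired t-tests (n = 20) at 0.3, 0.5 and 0.7: improvement about 23%, 18% and 13%.

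The two models together give about 13–23% for false improvement.

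**4. Readings with no inflation.**

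- First impression and mood must both succeed, each on one prespecified score: the chance of a false joint claim is no higher than that of one test.
- FIQ total alone is primary: 5% in either direction, 2.5% for improvement.

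**5. Comparison with power.** On the three-endpoint reading, the chance of at least one false improvement (5.5–7.3%) is close to the 8.1% chance of detecting the planned FIQ effect if it is real.

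**The case against.** The strongest defence is that Section 12.4 is mainly descriptive. The study is a 20-subject, single-centre, open-label post-market study, and no test is scheduled for any score. That is correct, and it limits the point: 14 is a count of available scores, not of planned tests. It does not remove the point. The same paragraph sets a significance level, 12.1 computes power at α = 0.05, and the synopsis states directional hypotheses. If no confirmatory test is intended, the plan should say so.

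A second defence is that the objective joins first impression with mood, which could mean that both must improve. With one named score each, that would remove the inflation. A third is that 10.1 and 12.1 make the FIQ the efficacy endpoint. Each reading is possible, but they differ from each other, and 12.3.1 lists three endpoints without choosing between them.

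A reader might infer something stronger: that 14 scores are each tested at 0.05, and that the chance of a false improvement claim is 13–14% rising to 51%. The documents do not support that. Those percentages count significant worsening as well as improvement, 51% requires 14 independent scores, and no section says that all 14 will be tested.

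**Conclusion.** The gap is real: three primary endpoints, a flat two-sided 0.05 level, and no named score, success rule or multiplicity control. Its size depends on a rule that the plan does not state.

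- Any one of three endpoints suffices: about 11–14% for a significant result in either direction (against 5%), and about 5.5–7.3% for false improvement (against 2.5%). This assumes correlations from 0 to 0.7.
- Free choice among about 14 scores: about 13–23% for false improvement at assumed correlations of 0.3–0.7. The independence figure of 29.8% is not an expected value. This case also assumes one SHS score.
- First impression and mood both required on one prespecified score each, or FIQ total alone primary: no inflation.

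The conclusion that the rule is missing does not depend on any assumed correlation.

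**What to change.** In 12.3.1, name one score per instrument: change from baseline to 14-Day Post-OCR in FIQ total, in SHS score and in HM Part I. In 12.4, test these three with Holm's procedure at an overall two-sided 0.05. Report the eight FIQ categories and HM Part II as estimates with 95% confidence intervals and no significance claim.

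The cost is wording, plus some power. At Holm's strictest step, 0.05/3 = 0.0167 (critical value 2.394), FIQ power on the plan's figures is Φ(0.565 − 2.394) + Φ(−0.565 − 2.394) = 3.4% + 0.2%, or about 3.5% before rounding, against 8–9% at 0.05. This is the worst case: if another endpoint is rejected first, the FIQ is tested at 0.025 or 0.05.

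The alternative costs the FIQ no power. Make FIQ total the sole primary endpoint at 0.05, as 12.1 implies, and move SHS and HM to secondary. This takes more than a change in Section 12: the primary objective and hypothesis in the synopsis, Section 5 and Section 10.1 all include mood and would have to be amended. Its price is that improved mood is no longer a primary claim.

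Whichever is chosen, 12.4 should state in one sentence what result counts as success, and this should be fixed before the outcome data are examined.
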